5. STUDY DESIGN

6.1 Summary of Study Design

This is a prospective, observational, non-invasive, crossover study. The participants will undergo CCT measurement using the Occuity PM1 device, Lenstar device, the Pentacam and then the Ultrasound pachymeter, which is standard of care. Measurement with ultrasound will occur last, as this will require instillation of anaesthetic drops which may confound the values obtained by the Occuity and other devices.

The participants will be recruited and will be measured by City University Clinicians. No additional visits will be required. The measurements will take place during their clinic appointment and will take approximately 30 minutes to complete.

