The ultrasound pachymeter (UP) is currently the gold standard method, as well as the most widely used to measure CCT. In comparative device studies, the ultrasound pachymeter has been shown to provide the most repeatable measurements. In addition, it is a small and portable handheld device, which makes it very convenient and timesaving to use during clinic appointments.

However, there are several negative aspects to the UP. First, it is necessary for the device to make direct contact with the cornea, which introduces the risk of corneal abrasions and subsequent infection. Second, anaesthetic eye drops need to be used for the patients to tolerate the corneal touch, and studies have shown that after instillation of anaesthetic eye drops, the CCT measurement is increased compared to before the use of anaesthetic, which can lead to a systematic over-reading of IOP. Third, the UP can be difficult to use, as it is necessary for the probe to contact the cornea perpendicularly, and exactly at the centre of the cornea to achieve the most accurate reading, which is difficult to achieve even with good staff training and experience. Lastly, despite the use of anaesthetic, measurement using this device

is uncomfortable, and sometimes poorly tolerated due to the corneal touch, especially by the paediatric population.

While there are optical devices available on the market which can measure CCT without the instillation of anaesthetic or corneal touch, they tend to be bulky machines which are not portable and require specialist training to use. This makes their use in busy hospital clinics and community optometry practices less feasible.

There is a clear need to develop a device which can measure CCT accurately without necessitating corneal touch and use of topical anaesthetic, as well as being easily portable. There is no such device available on the market currently, and in our search in the clinical trial databases and we did not identify any active trials investigating similar devices.

Occuity PM1 Pachymeter

The Occuity device is a new handheld, non-contact, optical pachymeter, which utilise a low power, eye safe near infrared (1310nm) beam to measure the corneal thickness.

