8. STUDY PROCEDURES

Only 1 study visit will be required.

The following procedures will be undertaken for the study, in time order:

1. Investigator to explain the study to patient, provide PIS, and obtain informed consent
2. CCT measurement using Occuity device
3. CCT measurement using Pentacam device
4. CCT measurement using Lenstar device
5. Instillation of Minims Proxymetacaine Hydrochloride 0.5% eye drops to the study eye
6. CCT measurement using Ultrasound Pachymeter

The devices will need cleaning between patients.

- The PM1 is to be cleaned with 70% isopropyl alcohol wipes to prevent patient-to-patient infection.
- The Lenstar device is to be cleaned with 70% isopropyl alcohol wipes will have the paper chin rest strip replaced.
- The Pentacam device is to be cleaned with 70% isopropyl alcohol wipes will have the paper chin rest strip replaced.
- The ultrasound probe will be wiped with a Q-tip soaked in 70% isopropyl alcohol. The tip will then be rinsed in sterile distilled water before use.

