11. RANDOMISATION

The volunteers will be randomised *a priori* into one of two sequences – those in Sequence 1 who follow the sequence Lenstar, Pentacam, PM1 then ultrasound and Sequence 2 who will follow the sequence Pentacam, PM1, Lenstar, ultrasound. The order in which subjects will be allocated to each sequence will be generated by a validated software prior to the start of the study to allocate the volunteers to each sequence.

NOTE: Ultrasound cannot be included within the randomisation as the anaesthesia required to undertake the US methodology would result in the Occuity PM1 & Lenstar measurements being unable to be recorded.

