15. INTERVENTIONS

15.1 Description of Study device

The Occuity PM1 device utilises both LED lights and low intensity infrared radiation. There are a total of 9 LED lights in a partial ring, the lights are at a radius of 8.75mm and spaced at 30° intervals. The total power is 2.4 mWm⁻² which is within the 10 mWm⁻² blue light hazard eye safety limit.

The infrared radiation is at a wavelength of 1310nm, and the maximum power is 50µW. The expected exposure to this radiation is less than 10 seconds in total, which makes it significantly under both the 2.5mW eye safe limit for 10 second exposure and the 158µW eye safe limit for 2-hour exposure, therefore the device is Class 1 eye safe according to BS EN 60825.

To take the measurement, the device will first be held above the study eye to achieve good alignment, after which the start button can be pressed to begin the measurement process. Once completed, the measurement will be displayed on the digital touchscreen of the device.

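### Nothing keeps the operator from knowing earlier readings on the same eye, or limits repeats, so agreement can be biased in the device's favour

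*Protocol*

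**What the plan says.** Section 6.1 puts all four devices into one visit of about 30 minutes and states: "The participants will be recruited and will be measured by City University Clinicians". It does not say whether one clinician takes all four readings on an eye.

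Two of the devices depend on the operator by the protocol's own account. For PM1, Section 15.1 says "the device will first be held above the study eye to achieve good alignment, after which the start button can be pressed", and then "Once completed, the measurement will be displayed on the digital touchscreen of the device". For ultrasound, Section 3 says that a perpendicular, exactly central contact is needed, "which is difficult to achieve even with good staff training and experience".

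The device order is stated in two ways. Section 11 randomises to "Sequence 1 who follow the sequence Lenstar, Pentacam, PM1 then ultrasound and Sequence 2 who will follow the sequence Pentacam, PM1, Lenstar, ultrasound". Sections 8 and 12 give a single order for everyone with PM1 first; in Section 8 the step directly after consent is "2. CCT measurement using Occuity device". Ultrasound comes last under either order: "Measurement with ultrasound will occur last, as this will require instillation of anaesthetic drops".

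Section 6.2 sets the criterion, Bland-Altman agreement of PM1 with Lenstar within ±20 µm. Section 4 (primary objective) and Section 17.2 (paired analysis) also cover ultrasound and Pentacam. Section 17.3 leaves the inclusion of spurious data to the chief investigator's discretion, without a criterion. The protocol is silent on masking operators to earlier values, on separate operators per device, on the number of readings, and on any rule for repeating or rejecting one.

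**The concern.** In an agreement study the result is the spread of the paired differences. An operator who knows what an eye has just read can judge a discordant reading to be misaligned and take it again, and let a concordant one stand. That acts in one direction only, towards agreement, which is the outcome that the sponsor needs. Randomising the order does not remove it, because whichever device comes later is the exposed one. Discarded attempts that were never recorded cannot be recovered by any analysis. For that reason this is a matter of conduct for the protocol and not one that a separate SAP could settle. The open discretion in Section 17.3 offers a second route to the same effect after the visit.

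**Working it through.** **1. Who is exposed to what.** The protocol gives no figure for this effect, so there is none to reproduce. Setting the stated orders side by side:

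| Order | Values existing when PM1 is read | Values existing when Lenstar is read | Values existing when ultrasound is read |
|---|---|---|---|
| Section 11, Sequence 1 | Lenstar, Pentacam | none | all three |
| Section 11, Sequence 2 | Pentacam | Pentacam, PM1 | all three |
| Sections 8 and 12 | none | PM1, Pentacam | all three |

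For the ±20 µm PM1-Lenstar criterion, PM1 can be drawn directly to the Lenstar value only in Sequence 1. In the other two orders it is the Lenstar reading that follows a displayed PM1 value. Ultrasound is fully exposed throughout but lies outside that criterion.

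**2. A simple calculation, near the upper end.** Assumptions, none from the protocol: no bias, SD of differences 10 µm, every reading more than 15 µm (1.5 SD) from the comparator retaken, and each retake a fresh draw of the whole difference.

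- Limits without retakes: 1.96 × 10 = ±19.6 µm.
- Share within ±1.5 SD: 0.8664; share retaken: 0.1336.
- Variance factor within ±1.5 SD: 1 − 2 × 1.5 × 0.1295 / 0.8664 = 0.552.
- Retaking until within 15 µm: SD factor √0.552 = 0.743, limits ±14.6 µm (26% narrower).
- One retake, second reading kept: 0.8664 × 0.552 + 0.1336 × 1 = 0.611, SD factor 0.782, limits ±15.3 µm (22% narrower).

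This overstates the effect. On a retake only the PM1 repeat error changes; the comparator reading and the eye-specific difference between methods stay. With the same 10 µm and 15 µm and one retake, the narrowing is 16% (±16.5 µm) if repeat error is half the variance and 9% (±17.9 µm) if it is a quarter. If only half the eyes are exposed, the 22%, 16% and 9% become 10%, 8% and 4%.

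**3. Repeat error separated from the rest.** The difference has variance sb² + sw² + sr², where sb is the between-eye SD of the method difference, sw the PM1 within-eye SD and sr the Lenstar within-eye SD (assumed 2 µm). A difference beyond a threshold triggers one retake that redraws only the PM1 error, and the closer reading is kept. Results by simulation, all discordant eyes retaken:

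| sw | sb | True bias | Limits, no retake | Threshold 20 µm | Threshold 10 µm |
|---|---|---|---|---|---|
| 3.6 | 3 | 0 | ±10.0 | ±10.0 | ±9.0 |
| 5 | 6 | 5 | −10.8 to 20.8 | −10.2 to 19.8 | −8.8 to 16.7 |
| 10 | 3 | 0 | ±20.8 | ±18.0 | ±13.6 |

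The unselected limits follow directly; for the last row, √(9 + 100 + 4) = 10.6 and 1.96 × 10.6 = 20.8. The narrowing runs from nothing (first row, 20 µm) to (20.8 − 13.6) / 20.8 = 35% (last row, 10 µm). In the second and third rows the limits start outside ±20 µm and end inside it.

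If only half the discordant readings are retaken, the effect is about half or less. The second row at 20 µm then gives −10.5 to 20.3 and still fails, while the third row gives about ±19.5 at 20 µm and ±17.6 at 10 µm and still passes.

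Section 3 reports a variation of about 10 µm between repeat PM1 readings without saying whether that is an SD, a range or a limit, so the third row can be neither confirmed nor excluded.

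**The case against.** A reader might infer that the clinicians do work with the other devices' values in view and that the endpoint is therefore biased. The protocol supports neither. Section 6.1 names only who measures, and in the plural, so separate operators are possible. Section 15.1 says that PM1 shows its own value, not that its operator sees anyone else's. Retakes are nowhere provided for. What can be said is that nothing prevents either.

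A reader might also take from "those in Sequence 1 who follow the sequence Lenstar, Pentacam, PM1 then ultrasound" that PM1 is always read against a known Lenstar value. That is Sequence 1 only. Under Sections 8 and 12 PM1 comes first, and no study value exists when it is read. The protocol does not describe Lenstar as depending on the operator in the way that PM1 and ultrasound do, so the pull on a later Lenstar reading may be weaker. A Pentacam value bears on the PM1-Lenstar difference only indirectly. Ultrasound, the most exposed device, is not in the ±20 µm criterion.

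The measurers come from a university and not from the sponsor, which limits direct sponsor influence. All of this stands, and it narrows the point. It does not close the gap: independence is not masking, and under each stated order at least one reading in the PM1-Lenstar pair can be taken with an earlier value for that eye known.

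**Conclusion.** The point holds as a gap in the plan. Operators are not masked to earlier readings, and repeats and rejections have no rule, so the agreement result can be biased towards success in a way that no later analysis could detect or correct. How far the PM1-Lenstar criterion is exposed depends on which of the conflicting orders is followed. Ultrasound is exposed under all of them, which matters for the primary objective and the paired analysis.

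The size is unknown. With assumed SDs, thresholds and retake rates, the limits narrow by between nothing and about a third, and some plausible combinations reverse the ±20 µm conclusion. Those figures show what is possible and are not an estimate for this study. The gap should be closed before recruitment; it does not by itself invalidate the design.

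**What to change.** Reconcile the device order in Sections 8, 11 and 12. Then add to Sections 8 and 12, for all four devices:

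- A reading is repeated only for a device error, or for a fixation or alignment failure noted before the value is read.
- Every attempt is recorded, and the analysis uses attempts according to that rule.
- Each device has its own CRF page, closed before the next device is used.
- Lenstar and Pentacam values are not viewed or transcribed until the PM1 and ultrasound readings are recorded, where the devices allow it. The protocol does not say whether they do.
- Where two clinicians are already present, the ultrasound operator is not the PM1 operator.

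In Section 17.3, require that decisions to exclude spurious data be made without sight of the other devices' values.

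The cost is a procedural paragraph and a revised CRF, with no extra staff. Results cannot be discussed with the participant until the end of the visit. With a single operator, memory of the displayed PM1 value is not fully removed, so the repeat rule and the log of attempts carry most of the protection.

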6.2 Primary and Secondary Endpoints/Outcome Measures

The central corneal thickness measurements taken by the three devices: Occuity PM1, the ultrasound pachymeter and Lenstar. Demonstrating that the Occuity PM1 Pachymeter is not inferior to the LenStar in terms of equivalency to a 95% confidence level using the Bland Altmen equation/approach based on +/-20micron equivalency.

Occuity outlines the target range of the PM1 to be within 300-800um. This is because we have already tested this target range with known artefacts. However, the patient population which

is being evaluated will consist only of patients with no known corneal abnormalities, corrective refractive surgeries, ocular inflammatory conditions etc.

It is likely that ~95% of corneal thicknesses which are measured will be within the range of 480um to 620um, therefore ~5% will be outside of the expected range. However, despite there being no history of the pre-stated conditions, there is still the likelihood of this study being able to assess patients with thick/thin corneas as part of the scope, as this is the percentage population who naturally have very thin or very thick corneas.

Secondary Endpoint

If evidence is not sufficient to demonstrate that the PM1 Pachymeter does not perform outside of the target range, it is understood that further investigation may be required. If it is deemed that further clinical investigation(s) are required, it is understood that a new MHRA application will be undertaken.

SAFETY OUTCOMES MEASURES

The type and number of adverse events, serious adverse events and any other device issues will be recorded. Adverse events and devices issues not reflected on the product label will be reported to the manufacturer and, for the Occuity product, will be dispositioned according to the Sponsor's complaint handling procedures for post-market products.

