4. AIMS AND OBJECTIVES

Primary Objective

To determine whether the Occuity PM1 device is non-inferior in measuring central corneal thickness when compared to ultrasound pachymetry, the Lenstar and the Pentacam.

Secondary Objective

The Investigation aims to assess long-term safety of the Occuity PM1 device when used under the conditions and for the purposes intended, to ensure it will not compromise the clinical condition or the safety of patients, or the safety and health of users or, where applicable, other persons.

If the evidence collected during this investigation is not sufficient to demonstrate that the PM1 Pachymeter does not perform under the conditions and for the purposes intended, it may be deemed possible that further investigation may be required. If it is deemed that further clinical investigation(s) are required, it is understood that a new MHRA application will be undertaken.

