17.2 Analysis of Endpoints

On completion of data collection, the primary endpoint will be analysed using paired tests or non-parametric equivalents, to compare the CCT measurement achieved using the ultrasound pachymeter and the Occuity PM1 device, and then between the values obtained from the Lenstar, Pentacam and Occuity PM1 device. The level of statistical significance will be set at $p < 0.05$.

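### Objective and analysis cover three comparators, the endpoint two and the success sentence only Lenstar, so one result can be both success and failure; the stated 0.95 power covers a single comparison

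*Protocol*

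**What the plan says.** Five places in the protocol bear on which comparison decides the study.

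- **Primary objective (section 4, repeated in the Synopsis).** PM1 is to be "non-inferior in measuring central corneal thickness when compared to ultrasound pachymetry, the Lenstar and the Pentacam". This is three comparators, joined by *and*.
- **Primary endpoint (section 6.2, repeated in the Synopsis).** "The central corneal thickness measurements taken by the three devices: Occuity PM1, the ultrasound pachymeter and Lenstar". The Pentacam is absent, although sections 6.1, 8, 11 and 12 all have it measured.
- **Success sentence (section 6.2, repeated in the Synopsis).** "Demonstrating that the Occuity PM1 Pachymeter is not inferior to the LenStar in terms of equivalency to a 95% confidence level". This is one comparator, to be judged by a Bland-Altman approach with a ±20 micron limit.
- **Analysis (section 17.2).** Paired tests or non-parametric equivalents at p < 0.05. The first step sets ultrasound against PM1. The second step brings in the other two comparators: "and then between the values obtained from the Lenstar, Pentacam and Occuity PM1 device". This is three comparators again, with no rule for combining the results.
- **Sample size (section 7, Sampling).** 163 eyes, alpha below 0.025, power 0.95, limit 2 microns. It has one limit and one sample size. It names no comparator, gives no SD and makes no allowance for several comparisons.

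**The concern.** Which comparison defines success is the core of a confirmatory claim, and here the answer depends on the section read. If PM1 agrees with the Lenstar and disagrees with ultrasound or the Pentacam, section 6.2 is met and section 4 is not.

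The protocol's own background makes such a split plausible. Section 3 says that anaesthetic drops raise the measured thickness, and sections 6.1 and 11 place ultrasound last, after the drops. A systematic ultrasound offset is therefore foreseeable, and whether ultrasound counts towards success could decide the outcome. If that is settled only after the data are seen, the choice is post hoc.

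The second consequence concerns power. A sample sized to give 0.95 power for one comparison does not give 0.95 for an objective that requires three.

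**Working it through.** **1. Comparator sets side by side**

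| Place | Ultrasound | Lenstar | Pentacam |
|---|---|---|---|
| Objective (Synopsis, section 4) | yes | yes | yes |
| Endpoint (Synopsis, section 6.2) | yes | yes | no |
| Success sentence (Synopsis, section 6.2) | no | yes | no |
| Analysis (section 17.2) | yes | yes | yes |
| Sample size (section 7) | one comparison, not named | | |

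There are three different sets. The objective and the analysis agree; the two sentences in section 6.2 are the outliers.

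**2. Reproducing the 163 eyes**

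Inputs from section 7: one-sided alpha 0.025 (read as one-sided because the design is non-inferiority), power 0.95, d = 2 microns, and n = f × 2σ²/d². The SD is not given, so it has to be assumed.

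- f = (1.960 + 1.645)² = 12.99.
- Solving 163 = 12.99 × 2σ²/4 gives σ = 5.01.
- With σ = 5: 12.99 × 2 × 25/4 = 162.4, rounded up to 163. An SD of 4.9 gives 157 and 5.1 gives 169.

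So 163 eyes fits one comparison with an assumed SD of 5. Its power is Φ(2/(5√(2/163)) − 1.960) = Φ(1.651) = 95.1%.

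**3. Joint power if all three must pass**

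Take 95% power for each comparison, as stated. This step does not need the value of the SD, only that each comparison reaches 95%.

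- Floor, with no assumption on correlation: 1 − 3 × 0.05 = 85%.
- Independent: 0.95³ = 85.7%.
- Common correlation 0.5 (trivariate normal): 88.2%.
- Common correlation 0.8: 90.7%.

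A correlation of 0.5 is what one expects if the three differences share only the PM1 reading and all devices have equal, independent errors: covariance σ², variance 2σ², ratio 0.5.

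**4. What 95% joint power would need**

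With SD 5, a 2 micron limit and no true difference, about 203 eyes (correlation 0.5) to 209 eyes (independent). At two eyes each that is 102 to 105 participants, against the planned 163 eyes and 82 to 100 participants.

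**5. Sensitivity of one comparison at 163 eyes, 2 micron limit**

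- True difference of 1 micron, SD 5: Φ((2 − 1)/0.554 − 1.960) = 44%.
- SD of 7.5 for one comparator, no true difference: Φ(2/0.831 − 1.960) = 67%.

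Joint power cannot exceed the power of its weakest comparison, so either departure takes it well below 86%.

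**The case against.** **The power range is conditional.** It needs each comparison to have exactly 95% power. Section 7 gives no SD and no comparator, so equal SDs are an assumption. If the ±20 micron figure of section 6.2 were instead applied to the mean difference with SD 5, every comparison would have power near 100%. This stands, and it is why 86–91% is given only under section 7's inputs. It does not rescue the stated 0.95, which would not describe a ±20 micron test either. The conflict between 2 and 20 microns is a separate matter.

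**A combining rule could sit in a statistical analysis plan.** That is fair for the detail, and no such plan is shown. But any rule it set would contradict either the objective or the success sentence in the protocol.

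**Stronger readings that the protocol does not support**

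- A reader might infer that objective, endpoint, success sentence and analysis all differ. They do not: section 17.2 covers the same three comparators as section 4.
- A reader might infer that success against any one comparator is enough, so that the error rate is inflated. At one-sided 0.025 per comparison the error would be 1 − 0.975³ = 7.3% if independent, falling to 4.9% at correlation 0.8. No section allows this: the objective joins the comparators with *and*, and the success sentence names one.
- A reader might treat the p < 0.05 tests of section 17.2 as three chances of a false claim. They are difference tests, and a significant result says that the devices differ. Several such tests raise the chance of falsely declaring a difference, not of falsely claiming non-inferiority.

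**Conclusion.** The contradiction holds on the text alone and needs no calculation: the same data can meet section 6.2 and fail section 4.

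The stated 0.95 power belongs to a single comparison. If all three must pass, which is the natural reading of the objective, joint power is about 86% to 91%, with a floor of 85%. This rests on 95% power for each comparison, and so on the 2 micron limit, equal SDs, no true difference and independent eyes. A larger SD or a systematic offset for any one comparator would lower it. No inflation of the error of the non-inferiority claim is shown.

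**What to change.** Use one comparator set and one decision rule in the Synopsis and sections 4, 6.2 and 17.2, and correct the three-device list in the endpoint. Two routes are open.

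- **(a) Keep the three-comparator objective.** Add the Pentacam to the endpoint, state that all three comparisons must pass, and restate the power in section 7 as below 0.95: about 86–91% under the assumptions above, with the SD given. The cost is a less favourable stated power. Holding 95% jointly would instead take about 203 to 209 eyes under those assumptions with SD 5.
- **(b) Keep the Lenstar-only success rule.** Reword the objective to match, name the Lenstar in section 7, and report ultrasound and the Pentacam as secondary, outside the confirmatory claim. This needs no more participants. The cost is that the claim no longer covers ultrasound, which section 3 calls the gold standard and section 6.1 the standard of care.

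Route (b) changes the primary objective and is not merely editorial, so the choice is the sponsor's and should be made before any data are seen. Under either route, section 7 should state the SD and use the same margin as the decision rule; otherwise no power figure describes the test that will be run.
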